The optimal theorized match for the identified high-risk subgroup is a combination of personalized pharmaceutical and personalized psychological interventions. This combined intervention versus a combined placebo condition is the primary comparison of interest for this study. We also will evaluate the individual effect of both the pharmaceutical and the psychological intervention. Such comparisons will provide important information on whether the active portion of the combined personalized intervention is truly BOTH pharmaceutical and psychological components, or whether one component is sufficient for effective pain relief to occur.

The high-risk subgroup is characterized by COMT genotype. COMT is a ubiquitously expressed detoxifying enzyme involved in a number of important biochemical pathways, particularly metabolism of catecholamines.⁴⁸ COMT encodes a

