
[figure not shown]
C2. Overview

Potential subjects will be screened and those meeting the high-risk criteria will be randomized into intervention groups. Treatment conditions will be administered for four consecutive days and statistical analysis will determine whether the combined personalized intervention group experienced shorter shoulder pain duration, lower peak pain intensity, or decreased upper-extremity disability (Aim #1) and determine which molecular, psychological, and pain sensitivity regulation mechanisms are associated with pain relief (Aim #2).

C3. Procedures

An overview of BISP study procedures is presented in Figure 5, and then described in more detail.

Figure 5. BISP Timeline and Study Procedures

Risk Subgroup Screening. We propose to enroll 448 high-risk participants, which will require prescreening approximately 3,000 people. In order to accomplish this we will conduct quarterly large-scale screenings on campus and in the local community (e.g. at local shopping malls, supermarkets, and community events) on a quarterly basis. We anticipate screening at least 200 people at each event for the first 4 years of the award (15 events total). At each screening, after providing informed consent, the participant will complete a brief screening questionnaire to determine eligibility and will be asked for permission to recontact. Members of the BISP team (Drs. [name] and [name]) have prior experience on screening this volume of participants

through their work on the Orofacial Pain Prospective Evaluation and Risk Assessment (OPPERA) study.⁵⁴ Eligibility will be determined from established inclusion and exclusion criteria from our initial funding period that establish appropriateness for the exercise-induced injury protocol, now modified to account for the risks of administering propranolol. Details of the inclusion and exclusion criteria are reported in the Human Subjects section. If eligible, each participant will provide a saliva sample and complete the Pain Catastrophizing Scale (PCS), a 13-item, 4-point rating scale.^{55, 56} A small incentive (\$5 gift card) will encourage participation. We have had success with similar approaches in the past for OPPERA.

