Primary Outcome Measures. The primary outcome measures were selected based on relevance to the clinical model and successful use in the initial funding period. Pain intensity ratings and self-report of upper-extremity disability will be used as primary outcome measures to determine efficacy for shoulder pain duration, peak shoulder pain intensity, and peak upper-extremity disability. ***These constructs have a conceptual link to chronic pain¹ and therefore can be used to characterize the presence of persistent or continued pain following exercise-induced injury.*** The Brief Pain Inventory (BPI) will be used to measure pain intensity as it has been found to have good test-retest reliability over short intervals.⁹⁷ The BPI consists of rating pain intensity on an 11-point numerical rating scale ranging from 0 (no pain) to 10 (worst pain intensity imaginable). The BPI asks subjects to rate current pain and pain at its worst, best and average over the past 24 hours. ***To determine recovery, subjects will complete the BPI daily until they rated their current pain at 0/10 and their worst pain was rated less than 2/10. The number of days it took to reach this recovery criterion will be recorded as duration of shoulder pain.*** The highest worst pain intensity recorded during recovery will be recorded as the peak shoulder pain intensity. The Disabilities of the Arm, Shoulder, and Hand Questionnaire (DASH) will be used to assess upper-extremity disability and we will continue to use a validated abridged version of the DASH (the QuickDASH) which consists of 11 functional items, with total scores ranging from 0 (not disability) to 100 (complete disability).⁹⁸ We will use the QuickDASH because shoulder pain can also affect distal function of the arm and hand, and we wanted to obtain a global upper-extremity assessment. Similar to the BPI ratings, QuickDASH scores will be recorded daily until recovery and the highest score during this period will be recorded as peak upper extremity disability. Another advantage of these measures is they are widely accepted as primary outcome measures in clinical studies, and were used as such in the initial funding period. Therefore, these measures will allow for specific effect size estimates for a subsequent randomized clinical trial in post-operative shoulder pain.

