
C4. Statistical Analysis Plan

All statistical analyses will be performed using the SAS software, version 9 (SAS Institute Inc, 1996). Summary statistics will be provided for baseline measures by intervention groups to determine if randomization produced balanced groups. Any group imbalance will be investigated further to determine if covariates should be considered. For Specific Aim #1, our primary analysis for efficacy will compare shoulder pain duration (i.e. *number of days until subject rated their current pain at 0/10 and their worst pain was rated less than 2/10*) across the four randomly assigned groups with the use of logistic regression. Consistent with the initial funding period, the primary outcome variable will be dichotomized based on duration of at least 7 days or not. There is an *a priori* plan to include age, sex, and race as covariates in this analysis, additional variables will be added as covariates only if imbalanced across groups and correlated with outcome measures. We anticipate very little missing data because this is a pre-clinical study, but any missing outcomes will be predicted by subject pain intensity trajectory plus baseline demographic factors. The primary comparison between the combined personalized intervention and the combined placebo condition will be tested at the 0.05 significance level, while the other five between group contrasts will be tested using a step-down procedure. For the other primary outcomes (peak pain intensity and upper-extremity disability as continuous measures) we will perform a similar analysis process (i.e. same considerations for post randomization imbalance, covariates, and missing data) with linear regression analysis to compare the four intervention groups. For Specific Aim #2, we will fit path models with predetermined orders to investigate the direct (intervention group) and indirect effects (through the mediating psychological, molecular, and pain sensitivity paths) of the randomly assigned condition on pain relief. The combined placebo intervention will serve as reference group for these analyses. The total, direct and indirect mechanistic effects on pain duration (dichotomous) and peak pain intensity and upper-extremity disability (continuous) will be estimated and tested at the 0.05 significance level for the comparison of assigned conditions. Specifically, the total effect will be estimated and tested through a logistic regression for pain duration and a general linear model for peak pain intensity, both of which include the assigned intervention conditions as independent variables while controlling for participant age, sex, and race. The direct effect will be estimated and tested with the use of the same models including the same independent variables, but controlling for mediating molecular, psychological, and pain sensitivity variables in addition to age, sex and race. The two regression models in the second step will reveal the contributions of the mediating psychological, molecular, and pain sensitivity variables on pain relief. On the other hand, the indirect effect will be calculated based on the difference between the total and direct effects. In addition, we will conduct a third

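### Three outcomes are called primary, but the plan has no rule for how they combine into the efficacy conclusion and no error control across them

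*Combined protocol and SAP*

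**What the plan says.** C1 (Rationale) fixes the group comparison: "This combined intervention versus a combined placebo condition is the primary comparison of interest for this study". It does not fix the outcome.

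C4 (Statistical Analysis Plan) does that in part. For Aim #1, "our primary analysis for efficacy will compare shoulder pain duration", and the same paragraph refers to a single primary outcome variable, duration dichotomised at 7 days. The primary contrast is tested at 0.05, "while the other five between group contrasts will be tested using a step-down procedure". The sample size section, also numbered C4, gives power for duration only.

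Three other statements widen the set of outcomes:

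- C3 (Primary Outcome Measures) says that the pain and disability ratings "will be used as primary outcome measures to determine efficacy for shoulder pain duration, peak shoulder pain intensity, and peak upper-extremity disability".
- C2 (Overview) states the Aim #1 question as whether the combined personalized group "experienced shorter shoulder pain duration, lower peak pain intensity, or decreased upper-extremity disability".
- C4 continues: "For the other primary outcomes (peak pain intensity and upper-extremity disability as continuous measures) we will perform a similar analysis process". It spells out what is carried over as "same considerations for post randomization imbalance, covariates, and missing data".

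The only significance level attached to the two continuous outcomes is in the Aim #2 text, where effects on "peak pain intensity and upper-extremity disability (continuous) will be estimated and tested at the 0.05 significance level for the comparison of assigned conditions".

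**The concern.** No section says whether efficacy requires duration alone, any one of the three outcomes, or all three. The step-down does not fill the gap. It ranks contrasts between groups, and even if it were carried over to each outcome, every outcome would still have its own unlinked 0.05 test of the primary contrast.

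The awkward result is a non-significant duration with a significant peak pain or disability. The text supports either conclusion, so the choice could be made after the data are seen. The text on the transition to the renewal application treats evidence of efficacy in this model as a precondition for a costly clinical trial. C5 also makes certain exploratory analyses conditional on Aim #1 showing no group differences, and that condition cannot be applied cleanly until the outcomes are ranked.

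**Working it through.** **Inputs from the sample size section.** 448 subjects in four groups; 40% with duration of at least 7 days under combined placebo and 20% under combined personalized; type I error 0.05; stated power 91%.

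**Assumed.** Equal allocation (448/4 = 112 per arm), two-sided tests, and a range of correlations between outcomes.

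**The plan's own figure.** With mean rate 0.30, power = Φ{[0.20 − z·√(2×0.30×0.70/112)] / √[(0.40×0.60 + 0.20×0.80)/112]} = Φ{[0.20 − z×0.0612]/0.0598}.

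- Two-sided 0.05 (z = 1.960): Φ(1.34) = 91.0%. The stated 91% reproduces.
- One-sided 0.05 (z = 1.645): 95.2%. The plan therefore appears to be two-sided.
- 0.05/3 = 0.0167 (z = 2.394): 81.4%.

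The 91% holds only if duration is tested at the full 0.05.

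**Error if any one outcome suffices.** Take three latent normal outcomes with common correlation r, and dichotomise duration at a 40% rate. Dichotomising attenuates the correlation of the duration statistic with each continuous statistic to r × φ(0.253)/√(0.40×0.60) = r × 0.386/0.490 = 0.789r. The two continuous statistics correlate at r. All three outcomes are null, each is tested at two-sided 0.05, and there are 4,000,000 draws:

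| Latent r | Any of three significant | Any, favourable direction | Peak pain or disability significant, duration not |
|---|---|---|---|
| 0 | 14.3% | 7.3% | 9.3% |
| 0.5 | 12.9% | 6.5% | 8.0% |
| 0.7 | 11.7% | 5.9% | 6.7% |
| 0.9 | 9.9% | 4.9% | 4.9% |

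The comparators are 5% for the second column and 2.5% for the third. The first row checks by hand: 1 − 0.95³ = 14.3%; 1 − 0.975³ = 7.3%; 0.95 × (1 − 0.95²) = 9.3%. At r = 1.0 the any-of-three error is still 7.9%, because the dichotomised outcome is not the same test. Simulating subjects at 112 per arm (60,000 trials) gave 14.0%, 12.8%, 11.5% and 9.8% for the any-of-three column. Applying the correlation directly to the test statistics, without attenuation, gives 12.5%, 10.9% and 8.4% at 0.5, 0.7 and 0.9.

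**Error if duration is tested first.**

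- All three null: 5.0% at every r, because no claim is possible without a significant duration.
- Duration truly effective at 91% power, the other two null, Holm across the two: at r = 0, 0.91 × (1 − 0.975²) = 4.5%; then 3.8%, 3.2% and 2.3% at r = 0.5, 0.7 and 0.9.
- The same, with both tested at 0.05 after duration and no Holm: at r = 0, 0.91 × (1 − 0.95²) = 8.9%; then 7.6%, 6.5% and 4.8%.

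**The case against.** The strongest reply is that the plan already has a hierarchy. It names one primary efficacy analysis, uses the singular for its primary outcome variable, and powers duration alone. Read that way, the error is 5% and the defect is a loose label plus an *or* in a one-sentence overview. This is the better-supported reading, and the inflation above does not apply under it. But it leaves unexplained why two more outcomes are called primary and are said to serve for determining efficacy. That phrase gives a purpose, not a decision rule.

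The upper end of the inflation needs uncorrelated outcomes, which is unlikely: the peaks are taken over the recovery period, and recovery itself defines duration. That is fair. At assumed correlations of 0.5 to 0.9 the multiple is about 2.6 to 2.0 rather than 2.9. The calculation also assumes that 0.05 applies to each outcome under Aim #1, which the plan does not state for the two continuous ones.

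A duration-first rule leaves the Aim #2 total-effect test of peak pain, which is close to the same regression (assigned condition with age, sex and race). That stands as a reason to say explicitly that the Aim #2 result cannot support an efficacy claim.

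Finally, the cost of gating depends on the true effect. With the power formula above, duration is non-significant in about 19% of trials at 40% versus 22.5%, 33% at 40% versus 25%, and 65% at 40% versus 30%. These alternatives are assumed, but the point is correct and the trial team should weigh it.

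**Conclusion.** The concern holds. The plan identifies a main outcome but does not say what the other two primary outcomes can establish, and it has no error control across the three. If duration alone decides, the error is 5%. If any one suffices, it is roughly two to almost three times that (9.9% to 14.3% for latent correlations of 0.9 to 0). This rests on two-sided tests at 0.05 for each outcome and on assumed correlations. If all three were required there would be no inflation, but joint power could not be computed because the plan gives no effect or standard deviation for the continuous outcomes. The sample size calculation itself is not in error. The point should be fixed before analysis; it does not invalidate the design.

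**What to change.** In C4, state that the efficacy conclusion rests on duration of at least 7 days, combined personalized versus combined placebo, at two-sided 0.05. Test peak pain intensity and peak QuickDASH for that same comparison only if duration is significant, by Holm across the two at 0.05 or in a stated fixed order. Then:

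- Reword the *or* in C2 and the primary-outcome labels in C3 and C4 to match.
- Keep the Aim #2 total-effect tests as mechanistic, and say that they carry no efficacy claim.
- Leave the step-down for the other five contrasts as planned, labelled secondary and outside this error control, so that the component comparisons promised in C1 are kept.

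Only wording changes. The 448 subjects and the 91% power for duration are unaffected. An equal three-way split of 0.05 would also close the gap, but it cuts the power for duration to 81%; restoring 91% would take 144 per arm (4 × 144 = 576 in total). The price of the ranking is that peak pain and disability are reported descriptively when duration is not significant: 1 − 0.91 = about 9% of trials at the planned effect, and more if the true effect is smaller.

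### For pain duration, the Aim 2 total effect retests at 0.05 two component-versus-placebo contrasts that Aim 1 places under a step-down procedure

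*Combined protocol and SAP*

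**What the plan says.** All the relevant text is under C4. Statistical Analysis Plan.

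**Aim 1.** Pain duration is compared "across the four randomly assigned groups with the use of logistic regression", and "the primary outcome variable will be dichotomized based on duration of at least 7 days or not". There is a "plan to include age, sex, and race as covariates in this analysis", and "additional variables will be added as covariates only if imbalanced across groups and correlated with outcome measures". On error control, combined versus placebo has its own test at 0.05, "while the other five between group contrasts will be tested using a step-down procedure". The step-down method, its order, and whether it depends on the primary result are not given.

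**Aim 2.** Combined placebo is the reference group. Total, direct and indirect effects on dichotomous duration, peak pain and disability "will be estimated and tested at the 0.05 significance level for the comparison of assigned conditions". For the first of these, "the total effect will be estimated and tested through a logistic regression for pain duration", with assigned condition as the independent variable and age, sex and race as covariates. Mediators enter only in the next step, for the direct effect.

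Nothing in that section or in C5 makes the Aim 2 total-effect test conditional on Aim 1, carries the step-down result forward, or calls the test descriptive. C5 item 4 describes only other Aim 2 analyses as more exploratory.

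**The concern.** With combined placebo as reference, the Aim 2 total-effect model has three condition coefficients: combined, drug-only and psychological-only, each against placebo. The last two are among the five contrasts that Aim 1 protects. The outcome, arms, kind of model and planned covariates are the same, but one aim applies a step-down and the other states a plain 0.05.

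The component contrasts matter to the trial's message. C1 (Rationale) says they will show whether both components are active or one is enough, and C3 (Primary Outcome Measures) says the outcome measures will supply effect sizes for a later clinical trial. A component could be reported as not significant for efficacy and, from the same data, as having a significant total effect.

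There is also a smaller gap. Aim 1 may add covariates for imbalance while the Aim 2 text fixes age, sex and race, so the two estimates need not be identical.

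**Working it through.** **Inputs.** N = 448 and long-duration rates of 40% (combined placebo), 30% (each single component) and 20% (combined), from C4. Sample Size Estimate and Study Timeline. Equal arms of 448/4 = 112 are assumed, because no numerical ratio is given. Tests are two-sided and without covariates.

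**Step 1: reproduce the plan's power.** Power = Φ[(d − z·se0)/se1], with se0 = √(2p̄(1−p̄)/n) and se1 = √((p1(1−p1)+p2(1−p2))/n).
- 40% v 20%: se0 = √(0.42/112) = 0.0612 and se1 = √(0.40/112) = 0.0598. Then (0.20 − 1.96×0.0612)/0.0598 = 1.34, so power is 0.910 (stated 91%).
- Four groups, 3 df: ncp = 112×(0.10²+0+0+0.10²)/(0.30×0.70) = 10.67, so power is 0.790 (stated 80%).

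The setting therefore matches the plan's own.

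**Step 2: one component v placebo, 40% v 30%.** se0 = √(0.455/112) = 0.0637 and se1 = √(0.45/112) = 0.0634.
- At 0.05: (0.10 − 1.96×0.0637)/0.0634 = −0.39, power 34.7%.
- At the first Holm step, 0.05/5 = 0.01: (0.10 − 2.576×0.0637)/0.0634 = −1.01, power 15.6%.

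The gap between these two thresholds is where the aims can disagree.

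**Step 3: false positives.** This is the chance that at least one of the two component-versus-placebo contrasts is declared significant when neither component works. It comes from simulation with 400,000 trials per scenario and Wald log-odds-ratio tests. If the two tests were independent, the unadjusted figure would be 1 − 0.95² = 9.75%. The shared placebo arm lowers it.

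| Rule | All arms 40% | Only the combination works (40/40/40/20%) |
|---|---|---|
| Aim 2, each at 0.05 | 8.8% | 8.8% |
| Aim 1, Holm over five | about 2.0% | 2.8% |
| Aim 1, Holm gated on the primary | 0.5% | 2.1% |
| Aim 1, fixed sequence after the primary | 0.9% | 3.8% |

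The Holm null figure is 1.9% with Wald tests and 2.1% with pooled z tests. If Aim 1 only ran unadjusted pairwise tests after a significant four-group test, the null figure would be 3.1%.

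**Step 4: disagreement under the planned 40/30/30/20% rates.** This is the share of trials in which at least one component is significant in Aim 2 but not in Aim 1.

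| Step-down variant assumed for Aim 1 | Share of trials |
|---|---|
| Holm over five, gated or not | 32% (about 18% for a given component) |
| Closed testing of homogeneity hypotheses | 21% |
| Fixed sequence | 16% |
| Pairwise tests after a global test only | about 2% (1.2% for a given component) |

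With the same model in both aims, the reverse pattern (significant in Aim 1 but not in Aim 2) never occurred.

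**The case against.** **Aim 2 is about mechanisms.** C2 and C5 assign efficacy to Aim 1 and mechanisms to Aim 2, and a total effect is the usual first step of a mediation analysis. Estimating it is indeed routine. But the plan also tests it, and it contains no mediator, so it is the efficacy contrast again. The plan does not say that an Aim 2 result would support an efficacy claim, and that use should not be presumed.

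**The 0.05 could be one 3-df test of the four conditions.** The wording allows this, and the null error of that test is 5.0%. Naming a reference group makes individual contrasts the more natural reading, but the text does not settle it. If a global test at 0.05 merely opened the way to unadjusted contrasts in Aim 2, disagreement with Holm in Aim 1 would still occur in 29% of trials at the planned rates.

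**The size depends on an unnamed method.** This stands, and it is why a range is given. The 2% end belongs to the variant with the weakest error control: once the combination works, the global test is usually passed on its account, and the component tests are then close to unadjusted.

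**Stronger conclusions a reader might infer, which the documents do not support:**
- *That 18% or 32% is an error rate.* Those figures assume both components work, so each such trial is one where Aim 2 detects a real effect that the step-down misses. Only Step 3 concerns error.
- *That the two verdicts point in opposite directions.* With the same model, the estimate and p-value are identical and only the threshold differs.
- *That peak pain and disability have the same conflict.* Peak pain is tested again in Aim 2 and disability is listed at 0.05. But the similar process described for these outcomes in Aim 1 lists imbalance, covariates and missing data, not the step-down. The detailed total-effect sentence also gives no model for disability.

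**Conclusion.** The concern holds for pain duration and for two of the five step-down contrasts. The plan states a protection for drug-only and psychological-only versus placebo in Aim 1, then states a second test of the same contrasts without it in Aim 2, and nothing connects the two. On the natural per-contrast reading with Holm, the false-positive chance for a component claim is about three to four times higher by the Aim 2 route (8.8/2.8 = 3.1 and 8.8/2.0 = 4.4). These sizes rest on equal arms of 112, no covariates and an assumed step-down method. All the variants tried give some disagreement.

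A reader might infer that the trial's main result is compromised. It is not: combined versus placebo is tested at 0.05 in both aims, so its error rate, its 91% power and N = 448 do not change. The three contrasts between active arms are not coefficients of the placebo-referenced Aim 2 model. The text should be corrected before analysis; no design change is needed.

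**What to change.** Add one sentence to Aim 2: the total effects on pain duration are the Aim 1 estimates, from the same model with the same covariates; they are reported with confidence intervals, carry the Aim 1 step-down verdict and are not tested again. Keep the Aim 2 tests for the direct and indirect effects.

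Two details make the sentence work. First, if Aim 1 adds covariates for imbalance, use the same set in the direct-effect model, because the indirect effect is taken as the difference between total and direct effects. Second, say that the intervals are not to be read as a further test, or the conflict returns through an unadjusted interval that excludes no effect.

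Naming the step-down method in Aim 1, and saying whether it also covers peak pain and disability, would remove the remaining ambiguity.

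The cost is a small text change, with no effect on sample size, data collection or primary power. The one loss is that Aim 2 no longer offers an unadjusted test of each component's total effect: under the planned rates, power for one component is 34.7% at 0.05 against 15.6% at the first Holm step.

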Secondary Outcome Measures. These measures represent underlying mechanisms that we hypothesize to be related to how the personalized interventions affect pain relief. These measures will be obtained at the same time each day (relative to the time of the initial shoulder injury) to avoid unwarranted variation.

Molecular: These measures will capture relevant inflammatory biomarkers. The low COMT activity of our high-risk group results in increased catecholamine activity, which augments release of proinflammatory cytokines under conditions of stress.⁹⁹⁻¹⁰¹ This catecholamine-evoked cytokine release can be attenuated by propranolol.⁹⁹⁻¹⁰² Moreover, catastrophizing, which also characterizes our high-risk group, has been associated with greater increases in circulating proinflammatory cytokines following both acute pain¹⁰³ and induction of pain-related negative emotions.¹⁰⁴ Thus, we hypothesize that personalized pharmaceutical or psychological intervention will significantly attenuate cytokine levels, with the greatest reduction observed in the combined personalized intervention condition. Moreover, because the increased pain evoked by COMT inhibition has been found to be mediated by increased circulating cytokines and reversed by blockade of beta-adrenergic (β 2 and β 3) receptors,⁷ we further expect that the attenuation of cytokine release will be associated with the efficacy of our combined personalized intervention for reducing pain and disability. Thus, we plan to perform assays for several inflammatory cytokines, including IL1B, IL6, IL8, and TNF α at baseline, immediately after the exercise-induced injury, and at regular intervals (Figure 5). All assays will be performed by the Metabolism and Translational Science Core of the Claude D. Pepper Older Americans Independence Center using commercially available kits with which they have extensive experience.

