
set of regression analyses to evaluate the effect of the assigned condition on the mediating variables which will determine which indirect paths are statistically significant.

C4. Sample Size Estimate and Study Timeline

A total of 448 high-risk subjects will be recruited. In the initial funding period we found that 40.5% of high risk subjects had pain duration \geq 7 days while 21.4% of the low risk group had long duration (Table 1). In our power analysis, we assumed that 40% of the combined placebo group will have long pain duration (rate for high risk subgroup), while the rate for the combined personalized intervention group will be 20% (rate for low risk group). Those with one personalized intervention were assumed to have 30% chance of having duration \geq 7 days. The planned sample size will enable us to have 80% power to detect the assumed differences across the four intervention groups and 91% power for the primary comparison between the combined personalized and the combined placebo interventions at a type-I error level of 0.05. The overall BISP timeline is in Table 3.

Table 3. Timeline and Key Periodic Events for BISP

Year 1		Year 2		Year 3		Year 4		Year 5					
Start Up	Quarterly Meetings with Research Team Annual Progress Reports to Institutional Review Board, Data Safety Monitoring Body, and NIH												
	Screening, Recruitment (annual rate = 96-120 participants), Intervention, and Follow Up												
	Scientific Conference		Scientific Conference		Scientific Conference		Scientific Conference		Scientific Conference				
On Site Consult		On Site Consult		On Site Consult		On Site Consult		On Site Consult	Analysis, Dissemination				

C5. Potential Pitfalls and Alternative Approaches

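### No Aim 2 mediation model includes a pre-treatment mediator value, although PCS is scored before randomization: a trait can pass as mechanism, and precision is lost

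*Combined protocol and SAP*

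**What the plan says.** C4. Statistical Analysis Plan sets out three sets of Aim 2 models. The total-effect models contain condition, age, sex and race. The direct-effect models are the same but "controlling for mediating molecular, psychological, and pain sensitivity variables in addition to age, sex and race". The indirect effect is total minus direct. A third "set of regression analyses to evaluate the effect of the assigned condition on the mediating variables" then decides which indirect paths count as significant; it lists no covariates. Effects "will be estimated and tested at the 0.05 significance level for the comparison of assigned conditions".

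No pre-treatment mediator value appears in any of these models. The section gives neither a time point for the mediators nor a choice between level and change. The rule for extra covariates is written for Aim 1 and admits a variable only if it is both imbalanced and correlated with outcome.

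What is measured, and when (C3. Procedures):
- **PCS.** At screening, eligible people "complete the Pain Catastrophizing Scale (PCS), a 13-item, 4-point rating scale". This precedes randomization and dosing.
- **Cytokines.** Assayed "at baseline, immediately after the exercise-induced injury, and at regular intervals".
- **Baseline session.** The Randomization and Personalized Interventions paragraphs put the first capsule before the injury, so that early drug effects on molecular and pain-sensitivity measures can be seen at this session. The psychological component runs on Days 2-5.
- **TSK-11 and FPQ-III.** The text gives no pre-dose time. Figure 5, which may, is not reproduced.

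**The concern.** Randomization protects the comparison of arms. It does not protect the link from mediator to outcome, because nobody is randomized to a mediator value. Anything that raises both a person's mediator and their pain confounds that link, even with perfectly balanced arms.

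Here a likely confounder is named in the plan. The progress section reports catastrophizing as a predictor of pain in both earlier cohorts, and a PCS cut-off defines the high-risk group. Someone who catastrophizes more at screening will tend to do so later and to hurt for longer, whether or not the later score does anything. If an arm also lowers PCS, as the plan hypothesises, total minus direct credits PCS with relief that it did not cause.

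A separate and milder cost falls on the regressions of mediator on condition. Stable between-person variance stays in the residual, so real effects on mediators are harder to detect.

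Identifying mechanisms is one of the trial's two aims and is meant to inform a later clinical trial.

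**Working it through.** **Inputs from the documents.** 448 participants and four arms; equal allocation is assumed, giving 112 per arm. Alpha is 0.05, taken as two-sided. Long-duration rates are 40% and 20%.

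**Assumed inputs (not in the documents).** Correlation ρ of baseline with later mediator, 0.5-0.7; correlation γ of baseline with outcome, 0.2-0.3; shift of the mediator by the arm, 0.3 SD; no effect of mediator on outcome; one mediator, two arms, standardised continuous outcome.

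**1. The plan's own figure.** The stated figure is "91% power for the primary comparison between the combined personalized and the combined placebo interventions". With pooled variance under the null: (0.20 − 1.96·√(2·0.30·0.70/112)) / √((0.24+0.16)/112) = (0.20 − 0.120)/0.0598 = 1.34, so power is 91%. It reproduces and confirms 112 per arm. No power is stated for Aim 2.

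**2. Precision of the arm effect on a mediator.** SE = √(2/112)·√(1 − ρ²); power for 0.3 SD = Φ(0.3/SE − 1.96).

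| Model | SE (SD units) | Power | Unadjusted n per arm to match, 112/(1−ρ²) |
|---|---|---|---|
| no baseline | 0.134 | 61% | 112 |
| baseline, ρ = 0.5 | 0.116 | 74% | 149 |
| baseline, ρ = 0.7 | 0.095 | 88% | 220 |

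Adjustment lowers the SE by 13% (1 − 0.866) to 29% (1 − 0.714).

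**3. False mediator-to-outcome link without baseline.** Within arm, mediator and outcome correlate at ργ through the trait alone: 0.5·0.2 = 0.10 up to 0.7·0.3 = 0.21. The test statistic is about √224·c/√(1−c²), with c that correlation: 1.50 and 3.21. Rejection is Φ(1.50−1.96) = 32% and Φ(3.21−1.96) = 89%. Multiplying by the 61% power on the other leg gives about 20% and 55% for both legs. Simulation gives 31-90% and 19-55%. The false indirect effect is 0.3·ργ, or 0.030 to 0.063 SD.

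**4. After adjustment.** If the measured baseline were an error-free copy of the only confounder, the mediator-to-outcome leg would reject at 5%, and both legs in about 4% (0.05 × 74-88%). With baseline reliability λ the remaining partial correlation is ργ(1−λ)/√((1−ρ²λ)(1−γ²λ)).
- λ = 0.8, ρ = 0.5, γ = 0.2: 0.020/0.880 = 0.023. The leg rejects at about 6%; with 71% power on the other leg, both legs about 5%.
- λ = 0.6, ρ = 0.7, γ = 0.3: 0.084/0.817 = 0.103. The leg rejects at about 34%; with 76% power on the other leg, both legs about 25%.

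**5. A harsher model.** Baseline and later mediator are two noisy readings of one trait (pre/post correlation r = 0.5-0.7), and the arm shifts mediator and outcome by −0.4 each. With trait loading 0.3 on the outcome and r = 0.7, the false indirect effect is −0.101, about 25% of the total effect; adjustment cuts it to −0.060. Over r = 0.5-0.7, both-leg significance falls from 78-81% to 38-43%. With loading 0.5 and r = 0.7 the bias falls from −0.165 to −0.097, but both-leg significance barely moves (84% to 82%).

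**6. If the arm does not move the mediator.** Both-leg significance stays near 5% without baseline, and the linear indirect effect averages zero.

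**The case against.** The best case for the plan is that it nowhere says it will use raw mediator levels. The Significance section speaks of changes in these processes, and the unseen Figure 5 may fix the timing. That stands: a reader might infer that the plan commits to unadjusted levels, and the text does not support this. What the text shows is that neither baseline adjustment nor change scores are specified. Change scores would not settle it either: in simulation they left false both-leg significance at 4-38%, against 19-54% for levels.

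Three further limits stand.
- The trait alone does not create mediation; treatment must also move the mediator. A reader might also infer that the condition-to-mediator estimates are biased. They are not.
- A return to about 5% after adjustment holds only for an error-free measure of the sole confounder.
- A clean pre-treatment value is established only for PCS. Baseline-session molecular and pain-sensitivity values may follow the first capsule. The text also conflicts on order: the Randomization paragraph places randomization before the injury, while the Exercise-Induced Shoulder Injury paragraph places the fatigue protocol before randomization. These passages must be reconciled.

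The assumed correlations may be too high for PCS, because entry requires a score of 5 or more and screening may precede Day 1 by some time. Pain duration is analysed as binary, whereas steps 3-6 use a continuous outcome. Both-leg significance is a yardstick used here; the plan's own path rule looks only at the condition-to-mediator leg.

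**Conclusion.** The point holds as an omission from a model list that is otherwise explicit. Where treatment shifts a mediator, a pre-existing trait can be reported as mechanism: both legs are falsely significant in about 19-55% of trials under the assumed correlations, and about 5-25% after adjustment at baseline reliability 0.6-0.8. The harsher model leaves more behind, with bias reduced by only about a third to two-fifths, so adjustment reduces the confounding and does not remove it. The condition-to-mediator estimates are unbiased, and their cost is precision alone.

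The correlations, reliabilities and shifts are all assumptions. The documents do not support concluding that Aim 2 is invalid, or that one covariate restores the nominal error rate. Aim 1 and its stated power are untouched. For PCS this is a free improvement.

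**What to change.** In C4. Statistical Analysis Plan, Aim 2:
- **PCS.** Add the screening score as a covariate in the condition-to-PCS regression and in the direct-effect models. Carry it in the matching total-effect models too, so that total minus direct compares like with like.
- **Cytokines, pain sensitivity, TSK-11, FPQ-III.** Add each mediator's baseline value only where it is confirmed to precede the first capsule. A value taken after the capsule but before Day 2 can serve only for contrasts that differ in the psychological component alone: psychological-only against combined placebo, and combined personalized against pharmaceutical-only. It cannot serve for combined personalized against combined placebo.
- **Definition.** State the time point of each mediator and whether level or change is used.
- **Interpretation.** State that adjustment reduces mediator-outcome confounding without removing it.

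Cost: SAP wording and one degree of freedom per mediator. PCS needs no new data. The other mediators need a check of measurement times against dosing, and some may prove to have no usable baseline for drug contrasts.
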